6.3 Pharmacokinetics/pharmacodynamics

As already mentioned these analyses will be postponed to the final analysis.

6.4 Safety

All subjects receiving any amount of study drug will be included in the safety analysis. Laboratory findings, AEs, concomitant medications, and medical history data will be provided in subject listings.

6.4.1 Adverse events

The investigator has to record on the respective CRF pages all adverse events occurring in the period between the signing of the informed consent form and the end of the follow-up phase. The original terms used by investigators to report AEs via the CRFs will be coded using the Medical Dictionary for Regulatory Activities (MedDRA).

For each AE, the number and percentage of subjects who experienced at least 1 occurrence of the given event will be tabulated according to the affected primary system organ class (SOC) and preferred term (PT) by dose cohort and dose actually received. A total column will be included in all safety summaries.

Frequency tables, showing an overall summary of number of subjects with drug-related AEs, SAEs and AESIs will be given, and will include the following information:

- maximum intensity for any AE,
- AE related deaths,
- AE resulting in permanent discontinuation of study drug,
- treatment emergent AE.

AEs will be considered treatment-emergent if they begin after the first administration of study drug and they do not start after more than 7 days after the last administration. Determination of whether or not an event is treatment-emergent will be derived after the missing or incomplete AE start date is imputed. In case an adverse event starts on the day of first administration of study drug and the time of onset is not known, the event is considered to be not treatment emergent, if it is reported to occur before the first dose of study drug. In all other cases the event is considered to be treatment emergent. Inhibitors will be defined as treatment-emergent if they develop after first study drug application. Imputation rules for missing and incomplete AE start are described in section 4.3.

6.4.2 Vital signs

Vital signs (systolic blood pressure (BP), diastolic BP, heart rate, respiratory rate, body temperature, body weight, and height) and change from baseline of vital signs will be summarized with descriptive statistics distinguishing pre-infusion and post-infusion readings. Post-infusion minus pre-infusion values will be summarized at Month 1, Month 2, Month 3, Month 4, and final visit in Part B.

6.4.3 Laboratory parameter

Laboratory values, incidence of high or low abnormal values, and changes from baseline will be summarized. In general only central laboratory values will be used for analysis. Where also local values are taken into consideration will be explicitly mentioned.

Two laboratory analytes, Anti HSP-70 and inhibitors, will be summarized in a listing that will include all values for those subjects with any positive result. Incidence of HSP-70 antibody formation and inhibitors will be assessed.

Inhibitor development, as measured by Bethesda assay will be summarized timepoint and presented in subject listings. The frequency of subjects who develop positive inhibitor titers (Bethesda ≥ 0.6 BU) as well as high titer (> 5.0 BU) will be presented. For the inhibitors as well as for the high titer inhibitors Kaplan Meier graphics for the occurrence will be provided.

A positive inhibitor testing is defined with a threshold of ≥ 0.6 BU in the central laboratory and a confirmation by

- a second plasma sample and a positive central testing or
- two consecutive local measurements (2^{nd} and 3^{rd} sample) with doubled threshold (Bethesda ≥ 1.2 BU).

In case a central value of the same samples used for local confirmation shows no inhibitor, the local confirmation is not valid.

High titer inhibitor needs not to be confirmed by a second high (> 5.0 BU) value, but the inhibitor itself needs a confirmation.

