In the event that any subject acquires an inhibitor to FVIII, Immune Tolerance Induction (ITI) will be offered. The subject may receive BAY 81-8973 up to 200 IU/kg daily or 100 IU/kg twice a day for 18 months. Treatment will be at the discretion of the treating physician, although the detailed treatment plan should be agreed with the Coordinating Investigator (as of Amd 7). Subject commences on ITI therapy will be followed up within the extension study. Data on treatment, FVIII measurements, and inhibitor levels will be collected. (as of Amds 1 and 6)

Primary variable

Annualized number of total bleeds (sum of spontaneous bleeds and trauma bleeds) within 48 hours (h) after a prophylactic infusion. (as of Amd 1)

Justification of the design

The study is designed according the requirements defined in the European "Note for Guidance on the clinical investigation of recombinant FVIII and FIX products" CPMP/BPWG/1561/99 and taking into account the revised draft version of this guideline CHMP/BPWP/144533/09⁽¹⁶⁾ (Committee for Proprietary Medicinal Products/Blood Products

Working Group; Committee for Medicinal Products for Human Use/Blood Products Working Party).

End of study

For each participating European Union (EU) country, the end of the study according to the EU Clinical Trial Directive will be reached when the last visit of the last subject (including subjects in the extension study) for all centers in the respective country has occurred.

The end of the study as a whole will be reached as soon as the end of the study according to the above definition has been reached in all participating countries (EU and non-EU).

The primary completion date for this study according to the Food and Drug Administration (FDA) Amendment Act is specified in a separate document (not part of this Clinical Study Protocol [CSP]).

5. Study population

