This SAP describes the objective, study design, analysis sets, all endpoints, and statistical analysis methods for the interim analysis of the part B of study 13400, where Previously Untreated Patients (PUPs) and Minimally Treated Patients (MTPS) where treated. Planned end was 50 exposure days (EDs), in case of inhibitor development the subjects should leave the study and get treatment in the extension part or outside of the study. Complete details of Tables, Listing and Figures (TLFs) specifications as well as dataset details and data handling

specifications will be provided in "TLF specifications" and "Analysis Datasets" documents which are an integral part of this SAP.

The analysis of the 6-month data for Previously Treated Patients (PTPs) in Part A is complete and reported in the clinical study report A51496. This SAP is applicable to completion of Part B. The extension study is ongoing.

The data upon completion of Part B will be analyzed later. The overall study will be closed after all subjects in Parts A and B have completed their respective extensions, in accordance with the protocol definition of 'end of study' (that is, last visit of the last subject [including subjects in the extension study]).

Further details can be found in the Clinical study protocol, which contains comprehensive information on the study drug.

2. Study Objectives

General objectives of this study are:

Primary objective

• To demonstrate the safety and efficacy of treatment with BAY 81-8973 for prophylaxis and breakthrough bleeds in children with severe hemophilia A

Secondary objectives

- To assess the safety and efficacy of BAY 81-8973 during surgeries
- To assess incremental recovery of BAY 81-8973
- To characterize pharmacokinetics in a subset of children

As during part B of this study, where PUPs and MTPs were treated up to 50 EDs (or development of inhibitor) only few recovery and pharmacokinetic data were collected, the last two secondary objectives will be analyzed in the final analyses of the study where more data are available.

3. Study Design

From the protocol:

This is a phase-III multicenter, open-label uncontrolled study to demonstrate safety and efficacy of treatment with BAY 81-8973 for prophylaxis, breakthrough bleeds, and surgeries in children with severe hemophilia A. The study will be conducted worldwide.

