4.2 Handling of Dropouts

In this study, all efforts must be taken to engage patients to comply with all study procedures and to continue to be followed until the end of the study.

A subject who discontinues study participation prematurely for any reason is defined as a "dropout" if the subject has received at least one dose of study drug. At the time of discontinuation, subjects should be requested to have a final visit to have performed the procedures and evaluations scheduled for the final study visit as described for last visit. Subjects who are withdrawn after the start of treatment will not be replaced.

A subject is regarded a "screening failure" if he terminates the study for any reason (e.g., failure to satisfy the selection criteria) prior to the time point used for the definition of "dropout".

In all cases, the reason for withdrawal must be recorded in the electronic case report form (eCRF) and in the subject's medical records.

The number of subjects who prematurely discontinue the study during the treatment phase or during the post-treatment observation phase for any reason, as well as the reasons for premature discontinuation of study, will be displayed.

Subjects who prematurely withdraw prophylaxis treatment due to inhibitor development will be considered premature discontinuations from Part B, even though they may continue with ITI treatment in the extension phase. For this reason a separate tabulation of the reason for premature termination will be given, where all reasons connected to ITI or inhibitors will be combined to "INHIBITOR MANAGEMENT". In addition subjects, who prematurely

discontinued part B without a clinical reason (inhibitor, AE) or withdrawal of informed consent or protocol violation, but just for logistical problems to match exactly the 50 EDs, will be counted as completers in this table.

Subjects can be withdrawn at their parent's request, or at the investigator's discretion due to, for example, development of inhibitory antibody or lack of compliance. The reasons for withdrawal will be listed. The annualized number of total bleeds will be calculated for these withdrawn subjects, and the time of the last procedure in a visit or the last infusion in the EPD will serve as the end time point used for calculation.

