4.4 Interim Analyses and Data Monitoring

The trial data is reviewed periodically by an independent Data Monitoring Committee (DMC). The DMC reviews certain safety and efficacy data sets as defined in the charter and provides written reports to the sponsor.

The 6 month data for PTPs was analyzed for regulatory purposes as a final analysis for Part A of the study. That analysis for PTPs is an interim analysis as defined in the protocol because the trial is ongoing for Part B and the extension phase. Safety was assessed in 20 PTPs before enrollment of PUPs began.

This SAP describes the interim analysis of part B of the study, originally planned for 25 PUPs. Amendment 3,6 and 7 of the protocol added up to 25 additional subjects to part B and the study was opened for MTPs. It will summarize data from Part B without extension phase. Extension study data will be described in the final CSR.

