6.2.2 Subgroup analysis

Subgroups of analysis are already described in 4.1:

- ➤ type of subjects: PUPs; MTPs; total
- inhibitor status: Subjects without inhibitor; Subjects with low titer inhibitor; Subjects without inhibitor or with low titer inhibitor; Subjects with high titer inhibitor
- > inhibitor status of PUPs: The same as above restricted to PUPs

These different periods for analysis are planned:

Period	Definition	To be used
Total part B period	MAINSDTM to MAINEDTM	always
		for response to
On-demand period	if OD_STDTM >. : OD_STDTM (is equal to	treatment of
	MAINSDTM) to OD_EDTM	bleeds

Statistical Analysis Plan PH-41074

Protocol No.: BAY	81-8973 / 13400
-------------------	-----------------

Page: 15 of 19:

Period	Definition	To be used
Prophy period (without once per week treatment)	if an infusion with EXSCATN = 8 exists and last infusion with EXSCATN = 8 < MAINEDTM: last infusion with EXSCATN = 8 to MAINEDTM. If last infusion with EXSCATN = 8 is at MAINEDTM no such period exists. If no infusion with EXSCATN = 8 exists: PX SDTM to PX ENDTM.	later for publications
Prophy period (including once per week treatment)	if SDTM > .: PX SDTM to PX ENDTM	always
Total treatment period (starting after 1st treatment)	TRTSDT to MAINEDTM	always
Period of once per week treatment only	if an infusion with EXSCATN = 8 exists: if OD_STDTM ne . then PX_SDTM to last infusion with EXSCATN = 8 else TRTSDT to last infusion with EXSCATN = 8	later for publications
Period of high inhibitor of high titer inhibitor subjects	if HINHSDTM < HINHEDTM: HINHSDTM to HINHEDTM	For extension only
Period of total inhibitor of high titer inhibitor subjects	if HINHSDTM > .: INHSDTM to INHEDTM	For extension only
Period of total inhibitor of low titer inhibitor subjects	if HINHSDTM = . and INHSDTM < INHEDTM: INHSDTM to INHEDTM	ABR & response to treatment

Further specification of the different periods are as following:

- The **total part B period** starts with the baseline visit and ends with the final visit. In case the study drug were already administered between the screening visit and the baseline visit, the period starts with the date of injection.
- The **on-demand period** starts with the first injection in an on-demand schedule and ends with the start of the prophylaxis period or final visit, whatever comes first.
- The **prophylaxis** period starts with the first and ends with the last injection of prophya ctic study drug.

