2.1 Secondary Endpoints

The secondary parameters are the following:

- Annualized number of total bleeds (sum of spontaneous bleeds, trauma bleeds, untreated bleeds, and 'other' bleeds) during prophylaxis treatment
- Hemostatic outcome of surgeries (both major and minor) including blood loss, transfusion, and/or hemostatic-related surgical complications
- Inhibitor development, as measured by Nijmegen modified Bethesda assay
- FVIII recovery values
- Pharmacokinetics (in a subset of children)

The annualized number of total bleeds will be calculated as described in section 4.5.2 of the SAP 2.0 and summarized accordingly.

The hemostatic outcome of surgeries will presented in a subject listings.

The incidence of inhibitor development during the total part B period will be presented in a summary table, additionally a subject listing will be provided relating the number of total exposure days to the corresponding FVIII Inhibitor value.

The FVIII recovery values will be calculated as described in section 4.7 of the SAP 2.0 and summarized accordingly. In addition, a subject listing will be provided.

The summary of pharmacokinetic values in Part B of the study will only be presented in the final report for the extension study due to the limited number of collected samples.

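### Part B inhibitor results stop at the Part B final visit, so a titre that passes 5 BU after an inhibitor-related exit is reported as low titer; the any-inhibitor count is exposed only in a narrow group

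*SAP*

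**What the plan says.** All SAP references are to the Part B SAP, version 2.0, and its supplement of 28 January 2020.

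- **What is reported.** Section 6.4.3: "The frequency of subjects who develop positive inhibitor titers (Bethesda ≥ 0.6 BU) as well as high titer (> 5.0 BU) will be presented". Kaplan-Meier graphics are planned for both. An inhibitor counts only if a central value of at least 0.6 BU is confirmed, either by a second central positive or by two consecutive local values (second and third sample) of at least 1.2 BU. A confirmed inhibitor becomes high titer on a single value above 5.0 BU.
- **Which data are used.** Section 4.4: "It will summarize data from Part B without extension phase". Supplement 2.1: "The incidence of inhibitor development during the total part B period will be presented in a summary table". Section 6.2.2 says that this period "starts with the baseline visit and ends with the final visit".
- **What an inhibitor does to participation.** Section 1: "in case of inhibitor development the subjects should leave the study and get treatment in the extension part or outside of the study". Section 4.2: "Subjects who prematurely withdraw prophylaxis treatment due to inhibitor development will be considered premature discontinuations from Part B", even if they go on to immune tolerance induction (ITI) in the extension.
- **What is collected afterwards.** Protocol section 4, on children offered ITI and followed in the extension: "Data on treatment, FVIII measurements, and inhibitor levels will be collected".
- **Where the classification is reused.** Sections 4.1 and 6.2.2 build the efficacy columns from inhibitor status: none, low titer, none or low titer, high titer.

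The SAP does not say whether a confirmatory or peak titre drawn after the Part B final visit counts in the Part B tables. It gives no censoring rule for the Kaplan-Meier graphics.

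**The concern.** The event being measured closes its own observation window. High titer is defined by the highest value reached, yet a child's Part B record ends because an inhibitor appeared, possibly while the titre is still rising. A value above 5 BU drawn a month later in the extension exists in the database but falls outside the stated scope.

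Inhibitor development is a named secondary parameter in the supplement, and the SAP introduction treats it as the leading complication of treatment. Part B gets its own planned analysis, so its high-titer frequency will be read on its own before the pooled analysis exists. A misclassified child also moves between columns of the bleeding tables.

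**Working it through.** **No figure to reproduce.** The documents state no inhibitor rate, precision or power for Part B, and SAP 9.1 says that no formal sample size was determined. The check is a walk through the possible cases, followed by an illustration on assumed inputs.

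**Cases under the stated scope**

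| Child | Any inhibitor in Part B table | High titer in Part B table |
|---|---|---|
| Confirmed, and above 5 BU, before or at exit | counted | counted |
| Confirmed at or below 5 BU before or at exit; above 5 BU later | counted | missed, shown as low titer |
| First positive at the 50-ED final visit; confirmed afterwards | not counted | not counted |
| Leaves after one positive, before a confirmatory sample | not counted | not counted |

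The third row can arise even when sites follow the schedule. Testing runs every 3-5 ED to 20 ED and then at 50 ED (protocol 7.1.2). The 30-40 ED interim visit has no inhibitor sample (protocol 7.1.2.7; Table 14.4b gives 0 ml). An inhibitor that arises after 20 ED without clinical suspicion is first found at the visit that ends the period.

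**Inputs for the illustration**
- N = 50: at least 25 plus about 25 (protocol 8.6).
- p, inhibitor rate: 50% is the upper value in the SAP introduction (up to half); 30% is an assumption.
- h, share of inhibitor children who ever exceed 5 BU: 40% or 70%, assumed.
- m, share of those who first exceed 5 BU after exit: assumed.
- u, share of inhibitor children without valid confirmation by the final visit: assumed.
- d, inhibitor-free children dropped from the denominator for fewer than 50 ED (the rule in protocol 8.3, which the Part B SAP does not repeat): assumed.

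**High titer.** True rate = p × h. Reported rate = p × h × (1 − m). Children moved = N × p × h × m.

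| p | h | True (m = 0) | m = 10% | m = 25% | m = 50% | Moved at m = 50% |
|---|---|---|---|---|---|---|
| 50% | 40% | 20.0% | 18.0% | 15.0% | 10.0% | 5.0 |
| 50% | 70% | 35.0% | 31.5% | 26.25% | 17.5% | 8.75 |
| 30% | 40% | 12.0% | 10.8% | 9.0% | 6.0% | 3.0 |
| 30% | 70% | 21.0% | 18.9% | 15.75% | 10.5% | 5.25 |

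At m = 0 there is no bias; for any m above 0 the reported rate is low.

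**Any inhibitor.** Reported rate = p × (1 − u) × N / (N − d), with p = 50%:
- u = 0, d = 0: 25/50 = 50.0%, no bias.
- u = 10%, d = 0: 22.5/50 = 45.0%.
- u = 20%, d = 0: 20/50 = 40.0%.
- u = 0, d = 5: 25/45 = 55.6%, too high.
- u = 10%, d = 5: 22.5/45 = 50.0%, the two effects cancel.

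**Kaplan-Meier curve for high titer.** The curve misses the same late crossings. If children who exit are carried as event-free, it is low in the same way as the frequency. If they are censored at exit, the children still at risk, who are mostly inhibitor-free, stand in for them. The censoring is then informative, and the curve is low whenever the children who left are the more likely to pass 5 BU.

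**The case against.** The strongest reply is that the planned order is positive test, confirmation, then exit. Protocol 7.5.3.4 and 14.5 require a second sample for every positive, and 14.5 makes ITI available once the inhibitor is confirmed. Protocol 6.1.5 defines clinically relevant inhibitor development as at least two positive titres with decreased recovery. The Final Visit also applies at early termination and includes an inhibitor sample (protocol 7.1.2.8), and SAP 4.2 asks children who discontinue to attend it. This stands. A reader might infer that both rates are biased low, but exit does not remove a confirmed inhibitor from the numerator. The any-inhibitor rate can also err upward if the 50-ED denominator rule is applied.

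A reader might also infer that the later titres are lost. For children in the extension they are collected, and protocol 8.5 plans an analysis of all main-study and extension data. They are lost only for children treated outside the study.

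Nor do all errors favour the drug. A high-titer child placed in the low-titer column would tend to worsen bleeding results there. The SAP's single-value rule for high titer is also wider than the persistence wording in protocol 8.3.

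Three further replies stand in part. Unconfirmed positives stay visible in listings, as serious adverse events and in the inhibitor-management tabulation, but that does not correct the summary rates. The variable behind the high-titer flag is derived in a separate dataset document, which may already use later titres; if so, the SAP text should say so. Extension titres may be drawn under ITI, which is a reason to flag them.

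**Conclusion.** The concern holds in limited form. Under the stated scope, the high-titer frequency can only be correct or too low from this mechanism, its Kaplan-Meier curve misses the same crossings, and the affected children sit in the wrong efficacy column. The any-inhibitor count is at risk only for children first positive at the 50-ED final visit or leaving before a confirmatory sample.

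The size cannot be determined from the documents. It is zero if no titre crosses 5 BU and no confirmation falls after exit. In the ranges tried, up to about 9 of 50 children move from high to low titer, but every value of h, m and u behind that is an assumption. The analysis is descriptive, so no test or error rate is affected.

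Counting unconfirmed first positives in the main result is a tempting further step. The documents do not support it, because protocol 8.3 counts inhibitors confirmed by repeat measurement.

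**What to change.** Amend SAP 6.4.3 and 4.1 and supplement 2.1 as follows.

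1. For any child whose first positive central titre falls in Part B, use all inhibitor results up to the data cut-off, extension samples included, to confirm the inhibitor and to assign high titer (any value above 5.0 BU).
2. Do not censor the high-titer Kaplan-Meier curve at an inhibitor-related Part B exit when later titres exist. State the rule for children without later titres.
3. Keep the confirmed count as the main result, and state its denominator.
4. Add as sensitivity results: the count that includes unconfirmed first positives with no later negative; the high-titer count from Part B samples only; and the number of children with no titre after exit.
5. Flag high-titer values drawn during ITI.

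The cost is SAP wording and a little reprogramming. No new sampling is needed for children in the extension. Some high-titer values will come from the ITI period, and the reported rates may be less favourable.
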